#### 5.4.4 Safety Endpoint

Drug safety will be assessed by examining adverse events, laboratory abnormalities, physical examination and ECOG performance status change from baseline. Adverse events, serious adverse events and abnormal lab values will be graded according NCI CTC criteria. Their occurrence within 30 days from the last study treatment will be summarized for all patients. We will monitor after the 9th, 18th, 27th, and 36th patient. We will stop for toxicity if more than 5 patients experience grade 4 or greater toxicity attributed as possibly, probably or definitely related to Denileukin diftitox after the 9th patient, more than 10 patients experience toxicity after the 18th patient, more than 15 patients experience toxicity after the 27th patient, and more than 20 patients after the 36th patient. For monitoring, toxicity will be defined over the 28 day period after treatment begins. If the probability of toxicity is 1/3, we will have a 5% chance of stopping the trial early based on the toxicity stopping rule. If the probability of toxicity is 0.60, we will have a 73.2% chance of stopping the trial early. If the probability of toxicity is 0.70, we will have a 94.7% chance of stopping early. If at any time during the conduct of the trial two patients die due to toxicity attributed to Denileukin diftitox accrual to the study will be placed on hold and modifications discussed with the sponsor before reopening the study.

- 5.4.5 We anticipate enrolling 10-12 patients per year into the Denileukin diftitox trial. Thus, if the trial goes to completion (2nd stage) at the 9 mcg/kg/d dose we anticipate enrolling the 29 patients in approximately 2.5 years. If the trial proceeds to completion through the 18 mcg/kg/d dose, a total of 38 patients will be enrolled in approximately 3.5 years.

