### *Design:*

- Nine patients will be treated initially with 9mcg/kg/d of Denileukin diftitox for five days, on an every two week schedule.
- Tumor response will be evaluated after two cycles of treatment. Stable or responding patients will continue treatment with evaluations every four cycles of treatment. Patients will be treated for two cycles beyond a complete remission.
- If no responses are seen at the 9 mcg/kg/d dose, and toxicity is acceptable, an additional 9 patients will be treated at a dose of 18 mcg/kg/d with the same statistical design.
- The trial uses an optimal 2 stage design targeting for a true response proportion > 30%. Nine patients will be treated initially at a dose of 9 mcg/kg/d, with expansion to 29 patients if a response is seen in one of the initial nine patients treated., If no response is seen at the 9 mcg/kg/d dose an additional 9 patients will be treated at a dose of 18 mcg/kg/d with expansion to 29 patients at this dose level if a response is seen. A stopping rule for excessive toxicity will be incorporated.

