#### 1.2.8 Proposed treatment plan

Patients with the chronic, lymphomatous and acute forms of ATL will be treated with 9 or 18  $\text{mcg}/\text{kg}/\text{d}$  for five days of Denileukin diftitox on an every two week schedule. Nine patients will be treated initially with a dose of 9  $\text{mcg}/\text{kg}/\text{d}$  with expansion to 29 patients if a response is seen in one of the nine initial patients treated. If no response is seen at this dose level, and if no excessive toxicity is seen, an additional 9 patients will be treated at a dose of 18  $\text{mcg}/\text{kg}/\text{d}$ . If a response is seen, this dose level cohort will be expanded to 29 patients. Tumor response will be evaluated after two cycles of treatment. Stable or responding patients will continue treatment

with evaluations after every four cycles of treatment for up to a total of 12 months of therapy. Treatment with Denileukin diftitox, beyond the 12 month time period is at the discretion of the Principal Investigator. Patients will be treated for two cycles beyond a complete remission.

Summary of results of treatment with denileukin diftitox at the 9 mcg/kg/d dose

Nine patients were treated at the 9 mcg/kg/d dose but no objective responses were seen. Evidence of anti-tumor activity was observed in leukemic patients where as evidenced by reductions in leukemic blood counts (Appendix 4). Two potential alternatives were considered; first, prolonged infusions at the same dose for 10 days and second, a higher dose of the agent. Denileukin diftitox was well tolerated in all patients with only one grade 3 non-hematologic toxicity of clinical importance, a supraventricular tachycardia associated with a cardiac troponin leak that resolved with medical management and did not recur with rechallenge. The toxicity observed at the 9 mcg/kg/d dose is summarized in Appendix 5. This proposed amendment will evaluate the other FDA approved dose of denileukin diftitox, 18 mcg/kg/d for 5 days, administered on an every other week basis to rule out a 30% response rate.

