### 5.4 Statistical Section

5.4.1 This study will include patients diagnosed with chronic, lymphomatous or acute ATL. Full lists of inclusion and exclusion criteria are presented in Section 2.2 and 2.3.

5.4.2 We will use an optimal two-stage design {Simon, 1989} to test for early evidence for efficacy based on complete and partial response. The design is based on the following: (a) the response proportion (partial and complete response) will be less than 5% if the treatment is totally ineffective ( $P_0=0.05$ ), (b) the treatment will be considered effective and worthy of future investigation if the true response proportion is  $> 30%$  ( $P_1=0.30$ ), (c) a type I error rate of 5% (i.e., the probability of concluding that the treatment is effective if the true response rate is 5% is 0.05), (d) a power of 95% (i.e., the probability of concluding that the treatment is effective if the true response proportion is 30% is 0.95).

In the first stage of the two-stage design, nine patients will be studied. If there are no partial or complete responses observed among the initial nine patients treated with a dose of 9 mcg/kg/d, the study will be expanded to an additional 9 patients at a dose of 18 mcg/kg/d. If one or more of the nine patients respond at either dose level, the study will proceed to a second stage. An additional 20 patients (i.e., a total of 29 patients in the trial) will be studied in the second stage at the same dose level. If four or more out of the 29 patients respond, the treatment will be deemed effective in early phase II development. The treatment will be deemed ineffective if fewer than four respond out of 29 patients.

With this design, there is a 63% chance of proceeding to the 18 mcg/kg/dose, if the response rate at 9 mcg/kg.dose is an ineffective 5%. Similarly, there is a 63% chance of terminating the study if the response rate at 18 mcg/dose/day is 5%.

The major objective of this study is to determine the anti-tumor activity of Denileukin diftitox with regard to response rate, time to progression, and overall survival. Response rate will be based on the number of patients who achieve either a complete or partial response to therapy. Time to progression will be measured from the date of registration until documentation of disease progression. Overall survival will be determined from the date of registration to the event of death or, for surviving patients, censored by the last day patients are known alive.

5.4.3 Antitumor Efficacy:

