## **7 DATA AND SAFETY MONITORING PLAN**

This protocol does not require a DSMB. The Principal Investigator shall monitor the trial by meeting on a monthly basis with the clinical trial team. The regulatory documents and Case Report Forms (CRFs) will be reviewed to verify adherence to good clinical practice procedures and to the protocol. The completeness, consistency and accuracy of the data entered on the CRFs shall be monitored. Copies of protocols, CRFs, original documentation of test results, correspondence, records of informed consent and other documents pertaining to the study will be kept on file in agreement with national regulation. The Principal Investigator is responsible for the safety and welfare of patients under their care and prompt identification, assessment and reporting of adverse events in accordance with protocol requirements. Safety data will be reviewed at other time points in response to adverse events felt to be medically significant.

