**DO NOT ADMISTER DENILEUKIN DIFTITOX THROUGH AN IN-LINE FILTER.**

Prepared solutions of denileukin diftitox should be administered within 6 hours.

The FDA approved recommended treatment regimen (one treatment cycle) is 9 or 18 mcg/kg/day administered intravenously for five consecutive days every 21 days. In this study denileukin diftitox at 9/mcg/kg/day or 18 mcg/kg/day shall be infused over 60 minutes for 5 consecutive days every 14 days. If infusional adverse reactions occur, the infusion should be discontinued or the rate should be reduced depending on the severity of the reaction. There is no clinical experience with prolonged infusion times (>80 minutes).

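### The toxicity stopping limits are not dose-specific: counted across both doses, the 18th-patient look cannot stop the trial even if all nine patients at 18 mcg/kg/d have grade 4 or worse toxicity

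*Combined protocol and SAP*

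**What the plan says.** Section 5.4.4 counts patients with grade 4 or worse toxicity that is at least possibly related to the drug and occurs within 28 days of starting treatment. The trial stops if the count exceeds 5 after patient 9, 10 after patient 18 ("more than 10 patients experience toxicity after the" 18th patient), 15 after patient 27 or 20 after patient 36. Dose is not mentioned. The stated chance of stopping early is 5% at a toxicity rate of 1/3 and 94.7% at 0.70; for the rate between them, "If the probability of toxicity is 0.60, we will have a 73.2% chance of stopping the trial early". Separately, two deaths attributed to the drug put accrual on hold.

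The Precis says that, if there is no response at 9 mcg/kg/d, "an additional 9 patients will be treated at a dose of 18 mcg/kg/d with the same statistical design". Section 5.4.2 caps each dose level at 29 patients. Section 5.4.5 gives the overall maximum: if the trial runs to completion at the higher dose, "a total of 38 patients will be enrolled in approximately 3.5 years".

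Section 1.2.8 reports that nine patients were treated at 9 mcg/kg/d without an objective response, and that "Denileukin diftitox was well tolerated in all patients with only one grade 3 non-hematologic toxicity of clinical importance". Appendix 5 has a single grade 4 entry for that cohort, a neutropenia.

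**The concern.** The next nine patients receive twice the dose of the first nine. Section 10.1.4 notes that "The FDA approved recommended treatment regimen (one treatment cycle) is 9 or 18 mcg/kg/day administered intravenously for five consecutive days every 21 days", whereas this trial repeats it every 14 days. A stopping rule is most needed at this step. If the counts run across both doses, a nearly clean first cohort dilutes the higher-dose cohort, and the 18th-patient limit may be out of reach whatever happens at 18 mcg/kg/d. The stated stopping probabilities assume one common toxicity rate, so they would overstate the protection when excess toxicity is confined to the higher dose.

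**Working it through.** **Which patients are counted.** One dose has at most 29 patients and the whole trial at most 9 + 29 = 38. A look after patient 36 can therefore occur only if both doses are pooled. No separate count limit is given for 18 mcg/kg/d.

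**Reproducing the stated probabilities.** Inputs are the limits above, cohorts of nine and one common rate p. At each look, add a Binomial(9, p) count to the running total, remove the paths that exceed the limit, and sum the removed probability. Each patient's 28-day outcome is taken as known at the look.

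| p | Stated | Looks 9, 18, 27 | Looks 9, 18, 27, 36 |
|---|---|---|---|
| 1/3 | 5% | 5.0% | 5.05% |
| 0.60 | 73.2% | 73.5% | 78.9% |
| 0.70 | 94.7% | 95.1% | 97.6% |

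The stated figures fit three looks at a single rate. They leave out the listed 36th-patient look.

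**What the pooled limits require at 18 mcg/kg/d.** Let x be the number of toxic patients carried forward from 9 mcg/kg/d. Appendix 5 gives neither attribution nor timing for its grade 4 entry, so x is 0 or 1.

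- Patient 18: at least 11 in total, so 11 − x of 9. That is 11 of 9 or 10 of 9, both impossible.
- Patient 27: at least 16 in total, so 16 of 18 (x = 0) or 15 of 18 (x = 1, 83%).
- Patient 36: at least 21 in total, so 21 of 27 (x = 0) or 20 of 27 (x = 1, 74%).

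The first look that can act comes after 18 patients at the higher dose.

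**Chance of stopping when the 18 mcg/kg/d rate is p.** The same recursion, started from x after nine patients, gives the pooled columns. The last two columns apply the limits to the 18 mcg/kg/d cohort alone.

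| p | Pooled, x = 0: by 27th / 36th | Pooled, x = 1: by 27th / 36th | By dose: at its 9th | By dose: by its 27th |
|---|---|---|---|---|
| 1/3 | about 0% | about 0% | 4.2% | 5.0% |
| 0.60 | 0.8% / 4.4% | 3.3% / 10.3% | 48.3% | 73.5% |
| 0.70 | 6.0% / 26.1% | 16.5% / 42.3% | 73.0% | 95.1% |
| 0.80 | 27.1% / 71.7% | 50.1% / 84.9% | 91.4% | 99.8% |

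**Expected number treated at 18 mcg/kg/d if the cohort would otherwise reach 29.** Subtract from 29 the patients spared at each look times the chance of stopping there. For p = 0.60:

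- Pooled, x = 1: 29 − 11(0.0328) − 2(0.0698) = 28.5
- By dose: 29 − 20(0.4826) − 11(0.1653) − 2(0.0870) = 17.4

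For p = 0.70 the values are 26.7 and 12.5.

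**Allowing for the efficacy stop.** If the true response rate is 5%, the cohort ends at nine with probability 0.95⁹ = 0.630, which is the 63% in 5.4.2. With response independent of toxicity, the expected number at p = 0.60 is 0.630 × 9 + 0.370 × 28.5 = 16.2 pooled, against 0.630 × 9 + 0.370 × 17.4 = 12.1 by dose. At p = 0.70 it is 15.5 against 10.3.

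**The case against.** The strongest objection is that pooling may not be intended. The stated probabilities match three looks, which is what one 29-patient dose level allows, and the Precis applies the same statistical design to the second dose. This is a fair reading, but it makes the 36th-patient look unreachable. The text is then still wrong, and two careful readers could treat the same nine patients differently.

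Three points on size stand in part:

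- **Ending at nine.** If the cohort closes at nine for lack of response, a look after the ninth patient spares no enrolment under either rule. At most it affects continued dosing. The saving in patients arises only if the cohort expands: about 4 to 5 patients on average at a 5% response rate, and about 11 to 14 if expansion is certain.
- **High rates.** The contrast is large only at high rates of related grade 4 toxicity, which the documents give little reason to expect. Section 1.2.7 describes mostly low-grade, transient toxicity at 18 mcg/kg every three weeks. However, 0.60 and 0.70 are the rates at which the protocol states its own protection, and the documents report no experience of 18 mcg/kg/d every 14 days.
- **Other safeguards.** The first cycle is given as an inpatient, doses can be reduced or stopped for individuals, and events are reported to the IRB. Under section 7, "The Principal Investigator shall monitor the trial by meeting on a monthly basis with the clinical trial team", with extra review of medically significant events. Nine of nine grade 4 events would probably not go unanswered. Apart from the two-death hold, though, none of these is a numerical rule for stopping a cohort, and the hold does not respond to non-fatal toxicity.

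Section 10 mentions a single patient on study at Amendment G, so the number still to be enrolled is uncertain. The documents do not say that accrual has closed.

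**Conclusion.** The concern holds. As written, with 0 or 1 events carried forward, the count rule cannot stop the trial on the first nine patients at 18 mcg/kg/d at any toxicity rate. If the cohort expands, the rule acts late and weakly: a 4.4% to 10.3% chance of stopping by the 36th patient at a true rate of 0.60, and 26.1% to 42.3% at 0.70. The stated 73.2% and 94.7% do not describe protection at this dose under the literal rule.

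The impossibility at the 18th patient is simple arithmetic and depends only on pooling and on Appendix 5 showing at most one patient with grade 4 toxicity. With two carried forward, the look could act, but only at nine of nine. The stopping probabilities also assume independent patients and a constant rate at 18 mcg/kg/d. At a true rate of 1/3 the two ways of counting differ little (about 0% against 5%). If per-dose counting was intended, the defect is an unreachable look and ambiguous text, and the same amendment cures it.

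**What to change.** Amend section 5.4.4 to say that toxicity is counted separately by dose. For 18 mcg/kg/d, stop if more than 5 of the first 9, more than 10 of the first 18 or more than 15 of the first 27 patients at that dose have qualifying toxicity. Delete the 36th-patient look. Give the stopping probabilities for that cohort at true rates of 1/3, 0.60 and 0.70: 4.2%, 48.3% and 73.0% if it ends at nine patients, and 5.0%, 73.5% and 95.1% if it reaches 27. Keep the two-death hold.

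The cost is one amended paragraph, with no extra patients or data. The downside is about a 5% chance of stopping the 18 mcg/kg/d cohort when its true rate is 1/3, which the protocol already accepts.

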## **6 HANDLING OF BLOOD AND TISSUE SAMPLES FOR RESEARCH PURPOSES**

### **6.1 By SAIC Frederick**

The Clinical Support Laboratory, SAIC-Frederick, processes and cryopreserves samples in support of IRB-approved, NCI clinical trials. The laboratory is located in a controlled access building and laboratory doors are kept locked at all times. Upon specimen receipt each sample is assigned a unique, sequential laboratory accession ID number. All products generated by the laboratory that will be stored either in the laboratory freezers or at a central repository facility are identified by this accession ID. An electronic database is used to store information related to patient samples processed by the laboratory. Vial labels do not contain any personal identifier information. Samples are stored inventoried in locked laboratory freezers and are routinely transferred to the NCI-Frederick repository facilities for long term storage. These facilities are operated by Fisher Bioservices, Inc. under subcontract to SAIC-Frederick. Access to stored clinical samples is restricted. Investigators establish sample collections under “Source Codes” and the investigator responsible for the collections, typically the protocol Principal Investigator, specifies who has access to the collection.

When requests are submitted by the NCI investigator for shipment of samples outside of the NIH it is the policy of the laboratory to request documentation that a Material Transfer Agreement is in place that covers the specimen transfer. The laboratory does not provide patient identifier information as part of the transfer process but may, at the discretion of the NCI investigator, group samples from individual patients when that is critical to the testing process. The NCI investigator responsible for the sample collection is responsible for ensuring appropriate IRB approvals are in place and that a Material Transfer Agreement has been executed prior to requesting the laboratory to ship samples outside of the NIH.

## **7 DATA AND SAFETY MONITORING PLAN**

This protocol does not require a DSMB. The Principal Investigator shall monitor the trial by meeting on a monthly basis with the clinical trial team. The regulatory documents and Case Report Forms (CRFs) will be reviewed to verify adherence to good clinical practice procedures and to the protocol. The completeness, consistency and accuracy of the data entered on the CRFs shall be monitored. Copies of protocols, CRFs, original documentation of test results, correspondence, records of informed consent and other documents pertaining to the study will be kept on file in agreement with national regulation. The Principal Investigator is responsible for the safety and welfare of patients under their care and prompt identification, assessment and reporting of adverse events in accordance with protocol requirements. Safety data will be reviewed at other time points in response to adverse events felt to be medically significant.

## **8 HUMAN SUBJECTS PROTECTIONS**

### **8.1 Rationale for Subject Selection.**

HTLV-I-associated ATL is a rare disease in the United States. Therefore, all subjects from both genders and all racial/ethnic groups are eligible for this study if they meet the

eligibility criteria outlined in Section 2.0. To date, there is no information that suggests that differences in drug metabolism or disease response would be expected in one group compared to another. Efforts will be made to extend accrual to a representative population, but in this preliminary study, a balance must be struck between patient safety considerations and limitations on the number of individuals exposed to potentially toxic and/or ineffective treatments on the one hand and the need to explore gender and ethnic aspects of clinical research on the other hand. If differences in outcome that correlate to gender or to ethnic identity are noted, accrual may be expanded or a follow-up study may be written to investigate those differences more fully.

The investigational nature and objectives of this trial, the procedures and treatments involved and their attendant risks and discomforts, potential benefits, and potential alternative therapies will be carefully explained to the patient and a signed informed consent document will be obtained.

## **8.2 Participation of Children**

Children will not be permitted to participate in this study although HTLV-I-associated ATL has been noted in individuals as young as nine years of age. There is no information on the toxicity of Denileukin diftitox in children.

## **8.3 Evaluation of Benefits and Risks/Discomforts**

The potential benefits to the subject are that the patient may undergo a partial or complete remission. Denileukin diftitox has demonstrated antitumor activity against CTCL and T cell NHL's. As noted above (1.2) it has been concluded concerning chemotherapy of ATL that "The various combination chemotherapies so far developed have not increased significantly the survival of patients with ATL." Furthermore, although therapy of ATL with AZT/IFN has been associated with partial and complete remissions, the median survival group of the patients treated was only 3 months whereas it was 13 months for patients with a complete or partial remission. Patients treated with Denileukin diftitox may experience infusion-related toxicities which can usually be managed effectively with appropriate pretherapy medication. Denileukin diftitox may cause immune dysfunction that predisposes to opportunistic infections. Prophylactic antibiotic and antiviral agents will be employed to reduce the risk of these complications. Denileukin diftitox is associated with vascular leak syndrome; therefore special precautions shall be undertaken to diagnose and manage this appropriately with supportive care.

## **8.4 Risks/Benefits Analysis:**

As just noted, toxicity due to Denileukin diftitox can be significant. All reasonable therapeutic interventions will be employed to prevent infusion related toxicity and the long-term consequences of immune suppression induced by treatment. There is a prospect for direct benefit for patients in that the use of Denileukin diftitox has led to remissions in other patients with IL-2R expressing malignancies. No cognitively impaired patients will be included in the study.

